4.6 Primary and Secondary Outcome Measures

Primary outcomes of this study include wound infection, wound dehiscence or fluid collection at the surgical site within 30 postoperative days (see Appendix for Classification of wound complications)

Secondary outcomes include pain, scar healing, quality of life, reoperation, duration and volume of wound drainage, graft function, hospital length of stay, clinical adverse events and mortality (see Appendix for NRS, POSAS, EQ 5D-5L and List of dependent variables).

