6 STUDY VISITS AND PROCEDURES SCHEDULE

Study Flow Chart

Timeline for follow up wound assessments:

Day 7 – The dressing is taken down for review and not replaced unless indicated. The review will include a microbiology swab (MCS); photo of the wound; modified ASEPSIS wound assessment; a pain assessment (NRS) and patient quality of life questionnaire (EQ-5D).

Day 14 – The dressing is taken down for review and not replaced unless indicated. The review will include a microbiology swab (MCS); photo of the wound; modified ASEPSIS wound assessment; a pain assessment (NRS) and the quality of life questionnaire (EQ-5D).

Day 30 (+/- 3 days) – The patient will present for follow up for an extended wound review by a study clinician or wound CNC, and a vascular sonographer. The review will include a modified ASEPSIS wound assessment; a photo of the wound; a pain and scar assessment (POSAS); a quality of life questionnaire (EQ-5D) and an ultrasound of the transplanted kidney which will also identify deep wound complications.

Day 90 (+/- 3 days) – The patient will present for follow up for wound review and ultrasound, which will include a photo of the wound; a scar assessment (POSAS); a quality of life questionnaire (EQ-5D) and an ultrasound of the transplanted kidney which will also identify deep wound complications.

Event	Day 0 Enrolment	Day 7	Day 14	Day 30 (+/- 3 days)	Day 90 (+/- 3 days)
Screening for Inclusion / Exclusion criteria	✓				
Participant Information Sheet and Consent Form (PISCF)	✓				
Routine perioperative data collection (Appendix C)	✓	✓	✓	✓	✓
Modified ASEPSIS wound assessment (Appendix B)		✓	✓	✓	✓
Photo of wound using REDCap App		✓	✓	✓	✓
Quality of life questionnaire (EQ-5D-5L) (Appendix D)		✓	✓	✓	✓
Microbiology swab (MCS)		✓	✓		
Pain Assessment (NRS) (Appendix G)		✓	✓		
Pain and Scar Assessment (POSAS) (Appendix E, F)				✓	✓
Ultrasound of Transplanted Kidney (Study specific)				✓	✓
Adverse Event & Serious Adverse Event Assessment		✓	✓	✓	✓

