9.3 Statistical Analysis Plan

Statistical analysis will be pre-specified and conducted according to both principles of intention to treat and per-protocol analysis, using SPSS version 20 (IBM, Armonk, NY, USA). Each incision will be randomized to the Prevena or standard dressing group. In the case that a patient requires bilateral incisions, both incisions will be allocated to the same treatment arm and counted as a single incision. Baseline characteristics of the two groups will be recorded and compared using Student's t-test and chi-square test for continuous and discrete data respectively. The primary outcome, the proportion of wound complications, will be compared between the Prevena and standard dressing groups using a chi-square test without Yates' continuity correction with a two-sided alpha of 0.05 at the final analysis using the Peto approach to preserve the overall significance level of 0.05 (23). An absolute risk increase/reduction for wound complications will be presented for the use of Prevena, as well as the number needed to treat in order to prevent specific wound complications. Patients lost to follow-up will be used in an intention-to-treat analysis with last observation carried forward.

The secondary outcome of identification of risk factors for wound complications will be assessed by multiple logistic regression of collected variables to assess their odds ratio. To prevent overfitting with the selected sample size, variables will be stepwise selected and also assessed for multicollinearity with the significance level of the dependent variables adjusted for multiplicity. Secondary outcomes will be compared between groups using a chi-square or Fisher's test for reoperation rate and delayed graft function and t-test for continuous variables, including the pain scale and quality of life. Non-normally distributed continuous variables will be tested for and compared using the Mann-Whitney *U* test. Survival analysis will be performed for allograft survival time with subjects without events censored at the 90 day final observation. A *p* value of less than 0.05 will be considered significant for the secondary outcomes and all tests will be two-sided.

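### Pain, scar and EQ-5D scores collected at two to four visits are compared by t-test or Mann-Whitney with no visit or contrast named, and missing scores are carried forward

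*Combined protocol and SAP*

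**What the plan says.** Section 4.6 gives the outcomes without a time point: "Secondary outcomes include pain, scar healing, quality of life, reoperation, duration and volume of wound drainage", followed by others. Section 6 sets the visits:

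- **Days 7 and 14:** NRS pain and EQ-5D. The Day 7 entry reads "a pain assessment (NRS) and patient quality of life questionnaire (EQ-5D".
- **Days 30 and 90:** EQ-5D again, and the table row "Pain and Scar Assessment (POSAS) (Appendix E, F". Appendices E and F hold separate observer and patient scales.
- **Day 0:** none of the three instruments is scheduled.

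Section 9.3 then states the analysis: "t-test for continuous variables, including the pain scale and quality of life". The next sentence gives the fallback: "Non-normally distributed continuous variables will be tested for and compared using the Mann-Whitney" U test. Scar scores are not named there. They fall under continuous variables, and no other method is given for them.

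On significance, a p "value of less than 0.05 will be considered significant for the secondary outcomes and all tests will be two-sided". The only multiplicity wording for secondary analyses, "with the significance level of the dependent variables adjusted for multiplicity", belongs to the risk-factor regression and not to these comparisons between arms.

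On missing data, Section 9.3 says "Patients lost to follow-up will be used in an intention-to-treat analysis with last observation carried forward". Section 9.1 applies the same rule to patients whose endpoints are not recorded.

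**The concern.** A t-test or Mann-Whitney test takes one value per patient. With two to four values per patient on each scale, the plan has to say which value, or which summary of them, is compared. It does this for other outcomes: 30 days for the primary outcome (Section 4.6) and censoring at 90 days for allograft survival (Section 9.3). For pain, scar and quality of life it leaves the choice open.

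Three things follow:

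1. **False positives.** The open choice allows several looks per scale at 0.05 each. Patients know their allocation (Section 5.4), so patient-reported scores have particular need of a fixed analysis.
2. **Precision.** A one-visit comparison leaves out the other visits, and also the site factor used to stratify randomisation.
3. **Carry-forward.** Where a later visit is missed, an early post-operative score is treated as if it were the later one.

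**Working it through.** **The plan's own figure.** No sample size or power is stated for these outcomes. The only sample-size figure is 239 per group for the primary endpoint (15% v 7%, two-sided 0.05, 80% power). It reproduces: the Section 9.1 formula gives 238.7, rounded up to 239. Nothing below changes it.

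**Inputs.** Visits per scale (Section 6): EQ-5D 4, NRS 2, POSAS 2. Alpha per test: 0.05 (Section 9.3). Planned size: 250 per arm (Section 4.3). The between-visit correlation r is not in the documents; I assume 0.3 to 0.8.

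**Number of tests if every visit is compared.** 4 + 2 + 2 = 8, or 10 if the POSAS observer and patient totals are tested separately.

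**Chance of at least one false positive.** With independent tests it is 1 − 0.95^k: 9.75% for k = 2, 18.5% for 4, 33.7% for 8 and 40.1% for 10. With correlated visits, it comes from simulated equicorrelated normal test statistics (400,000 draws, |z| > 1.96). The eight-test column takes the three scales as uncorrelated with each other:

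| r | EQ-5D, 4 visits | Two-visit scale | All 8 tests |
|---|---|---|---|
| 0.3 | 17.3% | 9.5% | 32.4% |
| 0.5 | 15.6% | 9.1% | 30.3% |
| 0.7 | 13.1% | 8.3% | 27.0% |
| 0.8 | 11.4% | 7.9% | 24.6% |

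If scales are correlated at about 0.3 with each other, the eight-test range is 30.0% down to 23.4%.

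**Precision.** The variance of an m-visit mean relative to one visit is (1 + (m − 1)r)/m. The one-visit standardised difference detectable with 80% power at 250 per arm is (1.960 + 0.842) × √(2/250) = 0.251. For the four-visit mean, multiply by the square root of the ratio:

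| r | Ratio, m = 4 | Detectable difference, m = 4 | Ratio, m = 2 |
|---|---|---|---|
| 0.3 | 47.5% | 0.173 | 65% |
| 0.5 | 62.5% | 0.198 | 75% |
| 0.7 | 77.5% | 0.221 | 85% |
| 0.8 | 85% | 0.231 | 90% |

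Testing all four EQ-5D visits with a Bonferroni correction would raise the detectable difference at any one visit to 0.299. The gains for the mean assume the same effect at every visit.

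**Carry-forward, by scale.**

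- EQ-5D: a Day 7 or 14 score can stand in for Day 30 or 90.
- NRS: only Day 7 for Day 14.
- POSAS: only Day 30 for Day 90.

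If a fraction f is missing in each arm, the estimated arm difference shifts by f × (early minus late arm difference among those missing). Section 9.1's rounding from 239 to 250 allows for f = 11/250 = 4.4%. At that level with equal loss, the shift is 4.4% of the early-to-late gap. If loss differs between arms, a further term appears, the difference in f times the change with recovery. The documents give no missingness figure for Day 90.

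**The case against.** The strongest reply is that the gap is narrow: name a visit for each scale and a t-test is adequate. Much of that stands. Several stronger readings are tempting and should not be drawn:

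- **That the plan will test every visit.** Section 9.3 does not say so, and one visit may be intended. The false-positive figures hold only if all visits are tested or the visit is chosen after seeing results. The text rules out neither.
- **That the t-test is invalid because scores within a patient are correlated.** At one visit there is one value per patient, so no independence assumption is broken. Leaving out site likewise costs precision and does not inflate error.
- **That a Day 7 score can replace Day 30 or 90 on all three instruments.** This is possible only for EQ-5D. NRS stops at Day 14 and POSAS starts at Day 30.
- **That repeated measures bring a large gain throughout.** The 37.5% cut in variance is for EQ-5D at r = 0.5. At r = 0.8 it is 15%, and for a two-visit scale it is 35% down to 10%. The device is worn for 7 days (Section 4.2), so a constant effect to Day 90 is far from assured.

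It can also be said that the carry-forward sentence in Section 9.3 sits with the primary outcome, and that loss is expected to be minimal. The first point fails, because Section 9.1 states the rule for unrecorded endpoints generally. The second stands in part: the daily follow-up cited there runs to 30 days and gives no assurance for Day 90.

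**Conclusion.** The point holds as a minor improvement to the secondary analyses. The documents name no visit or contrast for three repeatedly measured outcomes, and they prescribe carry-forward where observed visits could be modelled directly.

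The potential false-positive rate is conditional on testing all visits or choosing among them, and on the assumed correlations. The precision loss is conditional on those correlations and a constant effect. The carry-forward bias cannot be sized from the documents and may be small if missingness is as low as expected. A reader might infer that the trial's main conclusion is at risk. It is not: the primary test and the 239 per group do not depend on any of this.

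**What to change.** In Section 9.3, replace the t-test and Mann-Whitney wording for these scales with the following:

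1. Analyse each scale with a likelihood-based mixed model for repeated measures, with terms for arm, visit, arm-by-visit and site. Include no baseline term, since no Day 0 score is scheduled.
2. Use observed scores only, with nothing carried forward.
3. Prespecify one contrast per scale, either a named visit or the average over visits. The choice is the trial team's: averaging changes the question and could dilute an early effect.
4. State which POSAS score (observer, patient, or both) is tested. Do not pool NRS pain with the POSAS pain item as if they were one scale.
5. Report the other visits descriptively, with confidence intervals.

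This reduces 8-10 possible tests to 3, or 4 if both POSAS scores are tested, and returns the error rate to 5% for each prespecified contrast. It needs no new data or patients. The cost is a paragraph of SAP text, slightly more analysis and reliance on a missing-at-random assumption, which should be stated.

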The perioperative recipient management will otherwise be identical in both the intervention and the control arms and guided by site specific protocols. Data will be recorded daily until the date of discharge regarding site specific practices in regard to immunosuppression, antibiotics, imaging, drain management, and pathology results. If the patient is discharged with a drain, volumes must be recorded till the date of removal. If the patient re-presents to hospital with a wound complication, requires a re-operation or subsequent interventions, this is recorded for the requisite primary and secondary endpoints by the study investigators.

All patients will follow up at time points below, for assessments of the surgical site and overall health (see appendix). The date of drain removal and volumes drained will be confirmed and recorded if the patient was discharged with a drain. On review, patients may also undergo an ultrasound, or other suitable imaging at investigator discretion, to determine the presence of deep wound complications. Imaging staff will be blinded to the patients allocated treatment arm in the trial.

The timeline for patient follow up and assessment is as follows:

Day 7 – The dressing is taken down for review and not replaced unless indicated. The review will include a microbiology swab (MCS), photo of the wound, modified ASEPSIS wound assessment, a pain assessment (NRS) and patient quality of life questionnaire (EQ-5D).

Day 14 – The dressing is taken down for review and not replaced unless indicated. The review will include a microbiology swab (MCS), photo of the wound, modified ASEPSIS wound assessment, a pain assessment (NRS), and quality of life questionnaire (EQ-5D).

Day 30 (+/- 3 days) – The patient will present for follow up for an extended wound review by a study clinician or wound CNC, and a vascular sonographer. The review will include a modified ASEPSIS wound assessment, a photo of the wound, a pain and scar assessment (POSAS), a quality of life questionnaire (EQ-5D), and an ultrasound of the transplanted kidney which will also identify deep wound complications.

90 days (+/- 3 days) – The patient will present for follow up for wound review and ultrasound, which will include a photo of the wound, a scar assessment (POSAS), a quality of life questionnaire (EQ-5D), and an ultrasound of the transplanted kidney which will also identify deep wound complications.

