4.5 Expected Duration of Study

The study is expected to commence in January 2019 and conclude in 2021.

Expected duration of recruitment is 24 months and planned duration of follow up is 90 days.

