5.6 Participant Withdrawal

5.6.1 Reasons for withdrawal

Patients may withdraw from the study at any point, but will continue to be followed up and managed as per routine practice. Patient withdrawal may also occur due to loss of follow up, adverse event or death. Investigators may withdraw the patient from the study once the patient has been randomised, if the Investigator believes the allocated treatment arm is not in the patient's best interests, or the patient meets IFU related contraindications, however the reasons for withdrawal must be clearly documented.

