5.6.2 Handling of withdrawals

[figure not shown]
All participants withdrawn will ideally complete all study visits including Day 30 follow-up if able, as per routine clinical practice. Withdrawn patients will be included in an intention to treat analysis.

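### Allograft survival has Day 90 as its only censoring time, so patients whose graft status is last known earlier are, read literally, credited with unobserved graft survival (small effect, secondary outcome)

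*Combined protocol and SAP*

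**What the plan says.** Section 9.3 of the combined protocol and SAP has one sentence on this analysis: "Survival analysis will be performed for allograft survival time with subjects without events censored at the 90 day final observation". Section 4.5 sets the horizon: "planned duration of follow up is 90 days". No other censoring time appears in the text.

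For incomplete follow-up, section 9.3 says: "Patients lost to follow-up will be used in an intention-to-treat analysis with last observation carried forward". That sentence closes the paragraph on the primary outcome, but section 9.1 applies the same rule more generally, to patients whose endpoints are not recorded.

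The plan expects some patients to leave early. Section 5.6.1 says: "Patient withdrawal may also occur due to loss of follow up, adverse event or death". Section 5.6.2 adds "All participants withdrawn will ideally complete all study visits including Day 30 follow-up if able" and "Withdrawn patients will be included in an intention to treat analysis".

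Allograft survival is named among the secondary objectives in section 3.2. The outcome list in section 4.6 has "graft function, hospital length of stay, clinical adverse events and mortality". The text available for this review does not define the graft-survival event. It also does not include Appendix C, to which sections 6 and 7 refer for data collection and assessments.

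**The concern.** In a time-to-event analysis, an event-free patient contributes time only up to the last date on which the outcome was known to be absent. If everyone without an event is placed at Day 90, a patient last seen on Day 20 stays in the risk set for 70 further days in which a graft loss could not have been recorded. Carrying the last observation forward does the same thing, because it extends a functioning graft to Day 90.

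The error goes one way: graft loss is understated. It grows with the proportion leaving early, so unequal exits between arms would produce a difference where none exists, or mask part of a real one. Section 9.1 expects little loss to follow-up, but its reason is daily follow-up for 30 days. That leaves 60 of the 90 days, two thirds of the graft-survival window, without the same support.

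**Working it through.** **1. What the plan's own figures provide.** There is no event rate, hazard ratio or power for allograft survival. The nearest relevant figure is the allowance for loss in section 9.1. The sample size reproduces:

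(1.96 × √(0.11 × 0.89 × 2) + 0.84 × √(0.15 × 0.85 + 0.07 × 0.93))² / 0.08² = 238.7, rounded up to 239 per group.

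Raising 239 to 250 absorbs 11/250 = 4.4% early exits. The plan does not state this as a dropout rate; it is used below as one reference value.

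**2. Assumptions.** True graft loss by Day 90, L: 3% to 10%. Proportion leaving early, d: 2% to 20%. Constant hazard, exits uniform over Days 0 to 90, exits unrelated to graft loss.

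**3. Estimate under the literal rule.** With all event-free patients held to Day 90, the estimate is observed losses divided by patients randomised. With H = −ln(1 − L), its expected value is

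(1 − d) × L + d × (1 − L/H).

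For L = 0.05, H = 0.0513 and 1 − L/H = 0.0252. With d = 0.044: 0.956 × 0.05 + 0.044 × 0.0252 = 0.0478 + 0.0011 = 0.0489.

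| True loss | Exits 2% | Exits 4.4% | Exits 10% | Exits 20% |
|---|---|---|---|---|
| 3% | 2.97% | 2.93% | 2.85% | 2.70% |
| 5% | 4.95% | 4.89% | 4.75% | 4.50% |
| 10% | 9.90% | 9.78% | 9.51% | 9.02% |

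The understatement is about half the exit proportion in relative terms, and runs from 0.03 to 0.98 percentage points.

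**4. Simulation check.** 3,000 simulated arms of 250, with 5% true loss and 11 patients leaving early, gave a mean Kaplan-Meier loss of 5.00% when censored at last contact and 4.89% under the literal rule.

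**5. A worked arm with assumed counts.** Take 250 patients, 10 graft losses and 12 patients lost at Day 30. The literal rule gives 240/250 = 96.0%. Censoring the 12 at Day 30 gives 240/250 = 96.0% if all losses came before Day 30, and 228/238 = 95.8% if all came after. The shift is 0 to 0.2 points.

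**6. Unequal exits, no true difference.** With exits of 2% in one arm and 10% in the other, the literal rule gives 4.95% against 4.75% at 5% true loss (0.2 points), and 9.90% against 9.51% at 10% true loss (0.4 points).

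**7. Scale.** The standard error of a 5% loss in 250 patients is √(0.05 × 0.95/250) = 1.4 points. The 0.11-point error at 4.4% exits is less than a tenth of that.

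**The case against.** The strongest reply is that the sentence in 9.3 is ordinary wording for administrative censoring at the end of follow-up, and that the plan is merely silent on earlier exits. Keeping withdrawn patients in the intention-to-treat set does not settle the matter either, since membership of that set says nothing about a censoring date. This reading is possible. However, Day 90 is the only time given, and the plan's only rule for patients lost to follow-up carries the last status forward. An analyst following the text would arrive at Day 90, and under the milder reading the same sentence still has to be added.

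Second, many early exits would do no harm. Section 5.6.1 has withdrawn patients continue under routine follow-up, section 5.6.2 asks them to complete visits where able, and the electronic medical record is a data source. Where Day 90 status is truly observed, censoring at Day 90 is correct. Similarly, completers seen within the visit window ("90 days (+/- 3 days) – The patient will present for follow up for wound review and ultrasound") are at most three days off, which is negligible. The point is therefore limited to patients truly lost, or withdrawn without further follow-up.

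A reader might go further and infer that patients who die with a functioning graft are entered as graft survivors to Day 90. The documents do not support that as a finding. The event is undefined in the available text, death may count as an event, and Appendix C might say so. Any large shift obtained by recounting deaths as failures would come from the event definition, not from the censoring date. Nor would a difference in deaths between arms be lost from the report, because mortality is a separate secondary outcome.

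**Conclusion.** The rule is wrong as written, at the lowest severity. Taken literally, section 9.3 and the carry-forward rule credit unobserved graft survival to patients whose status is last known before Day 90. The bias favours graft survival, and favours it more in the arm with more early exits.

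The effect is small: about 0.1 point at 5% true loss with exits at the level the sample size allows for, and just under 1 point only at 10% loss with 20% exits. These figures rest on assumed rates, a constant hazard and exits unrelated to graft loss. If patients leave because the graft is failing, the bias could be larger, and censoring at last contact would not remove it either. Only a secondary outcome is touched; the primary endpoint and the 239 (250) per arm stand. The handling of death with a functioning graft is a point to clarify, not a demonstrated error.

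**What to change.** In section 9.3, replace the censoring rule with two statements: event-free patients are censored at the last date on which graft status was known, at most Day 90; and last observation carried forward does not apply to this time-to-event outcome.

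For each patient who withdraws or is lost, record the last known graft status and its date from the electronic medical record already used for data collection (sections 4.2 and 10.1), as far as consent allows. This shortens the unobserved time and is the better protection if exits are related to failing grafts.

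As a clarification in the same place, define the graft-survival event and say whether death with a functioning graft is an event, a censoring or a competing event. If Appendix C already does so, a cross-reference is enough.

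The cost is a few sentences and fields for one date and one status. The sample size does not change, and reported graft survival may be very slightly lower.

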3.2 Secondary Objectives

Secondary objectives of this study include identification of risk factors for wound complications at the surgical site, as well as reoperation, prolonged hospital stay, allograft survival, delayed graft function. This study will also assess pain, scar healing and quality of life in each treatment arm, and aim to complete a cost-benefit analysis of the Prevena device in renal transplantation.

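### Section 9.3 calls any between-arm secondary outcome significant at two-sided p<0.05, with no hierarchy, gate, adjustment or supportive label, so isolated false secondary claims are likely

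*Combined protocol and SAP*

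**What the plan says.** Section 4.6 lists the secondary outcomes in two runs: "Secondary outcomes include pain, scar healing, quality of life, reoperation, duration and volume of wound drainage", then "graft function, hospital length of stay, clinical adverse events and mortality". Section 3.2 divides graft function in two, naming "reoperation, prolonged hospital stay, allograft survival, delayed graft function", and adds "This study will also assess pain, scar healing and quality of life in each treatment arm".

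Section 9.3 assigns the tests: "chi-square or Fisher's test for reoperation rate and delayed graft function and t-test for continuous variables, including the pain scale and quality of life". It adds Mann-Whitney for non-normal data and a survival analysis of the allograft to day 90. It then closes with the decision rule that a p "value of less than 0.05 will be considered significant for the secondary outcomes and all tests will be two-sided".

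Multiplicity is mentioned in two other places:

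- **Risk-factor regression (9.3).** The sentence on stepwise selection and collinearity says that a significance level is adjusted, without naming a method.
- **Peto approach (9.3 and 9.4).** This uses p=0.001 at the interim and 0.05 at the end, and covers only the primary outcome.

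Section 9.3 also promises "the number needed to treat in order to prevent specific wound complications". It attaches no interval and no descriptive label to these results.

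**The concern.** The plan is not silent here. It gives an explicit instruction that applies equally to pain, scar, quality of life, drainage, length of stay, reoperation and graft outcomes. Followed exactly, it allows the report to declare a significant benefit or harm on any one of them, even when the primary test is negative.

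Both patients and treating staff know the allocation (section 5.4), and publication is intended (section 12). An isolated significant result on pain or length of stay could therefore become the message of a trial whose primary result was null. A reader would have no pre-stated basis for discounting it. The authors did protect the overall level for the primary outcome, which makes the lack of any statement for the secondary outcomes more noticeable.

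**Working it through.** **Plan's own figure.** The documents state no family-wise error rate for the secondary outcomes; the only level given is 0.05 per test. The sample-size figure in section 9.1 reproduces: (1.96·√(0.11·0.89·2) + 0.84·√(0.15·0.85 + 0.07·0.93))² / 0.08² = 238.7, so 239 per group. It concerns the primary outcome only and plays no part below.

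**Step 1: count the outcomes, one test each.**

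- From 4.6: pain, scar healing, quality of life, reoperation, drainage duration, drainage volume (6).
- From 4.6: graft function, length of stay, adverse events, mortality (4, running total 10).
- From 3.2 and 9.3: graft function becomes delayed graft function and allograft survival (total 11).
- Section 9.3 names no test for adverse events or mortality, and these are better described than tested. Setting them aside leaves 9.

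The appendix list of dependent variables that 4.6 points to is not in the text available for this review, so the count rests on these three sections.

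**Step 2: independent tests, all nulls true.** P(at least one p<0.05) = 1 − 0.95^k.

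- k = 9: 1 − 0.95^9 = 0.370
- k = 11: 1 − 0.95^11 = 0.431

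**Step 3: correlated tests.** The documents give no correlation, so a range is assumed. For k normal test statistics with common correlation ρ, the rate is 1 − ∫ [Φ((1.96 − √ρ·x)/√(1−ρ)) − Φ((−1.96 − √ρ·x)/√(1−ρ))]^k φ(x) dx.

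| Outcomes | ρ = 0 | ρ = 0.2 | ρ = 0.5 | ρ = 0.8 |
|---|---|---|---|---|
| 9 | 37% | 35% | 27% | 17% |
| 11 | 43% | 40% | 30% | 18% |

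**Step 4: sparse outcomes.** Fisher's test is conservative when events are few. With 250 per arm, its true size at nominal 0.05 is about 0.8% for an assumed event rate of 1% and about 2.1% for a rate of 2%. As an illustration, if two of nine independent outcomes had a size of 0.8%, the rate would be 1 − 0.95^7 × 0.992² = 0.313 instead of 0.370.

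**Step 5: sensitivity to the count.** With only 6 outcomes the rate is 26%, 21% and 14% at ρ = 0, 0.5 and 0.8. In the other direction, repeated visits, the two POSAS scales and the paired intention-to-treat and per-protocol analyses would add tests, though strongly correlated ones.

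**The case against.** **The existing wording may already cover these outcomes.** The regression sentence speaks of adjusting the significance level of dependent variables, and section 4.6 uses the term dependent variables for an appendix list connected with the secondary outcomes. The phrase is therefore ambiguous. Its place in a sentence about overfitting and stepwise selection makes the regression reading the natural one. If it was meant to reach further, it conflicts with the flat p<0.05 rule that follows. The text needs clarifying on either reading.

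**The plan never promised 5% across the family.** This stands. A reader might infer that a stated 5% error rate is really about 30%. The documents do not support that: 0.05 is the level of each secondary test, an overall level is claimed only for the primary outcome, and 30% is simply the value for 11 outcomes at an assumed correlation near 0.5.

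**The trial rests on one primary outcome.** This also stands. The sample size and the alpha control concern that outcome alone, and nothing in the plan says its conclusion may rest on a secondary one. That limits the weight of the point, but the rule still authorises calling a secondary result significant.

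**The numbers needed to treat.** A reader might infer a further uncontrolled family of claims, one for each of the eight classes in Appendix A. The text does not go that far. Section 9.3 says only that these figures will be presented, with no significance rule, and does not cite Appendix A there; section 4.6 names three types of complication. Simulating eight independent classes at 3% each would imply an overall rate of 1 − 0.97^8 = 21.6%, against the planned 15%, and several classes overlap clinically. No figure for this is offered here. What remains is that these results lack an interval and a descriptive label.

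**Conclusion.** The point holds as a gap in the decision rule for the between-arm secondary outcomes. Under the plan as written, with no true effect on any of the 9 outcomes left after setting aside adverse events and mortality, at least one would be called significant with probability of about 37% under independence, 27% at a correlation of 0.5 and 17% at 0.8. For all 11 the figures are 43%, 30% and 18%.

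These figures assume one test per outcome, a true size of 5% for each test, and a common correlation that the documents do not give. Sparse outcomes pull the figures down; extra visits and scales push them up. No single value should be quoted as the plan's error rate.

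It would be wrong to infer that the primary conclusion is compromised. The primary test, its interim provision and the sample size do not depend on this rule. The change should be made, but it is a matter of reporting discipline and not a flaw in the design.

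**What to change.** In section 9.3, and wherever the rule is repeated, replace the sentence on significance of the secondary outcomes with:

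> Secondary outcomes are supportive; between-arm differences will be reported with 95% confidence intervals not adjusted for multiplicity, and no efficacy claim will rest on them. All tests are two-sided.

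Also:

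- If the sponsor wants a confirmatory secondary claim, name the k outcomes concerned. Test them only after a significant primary result, by Holm at an overall two-sided 0.05. The smallest p-value is then compared with 0.05/k; for all nine, 0.05/9 = 0.0056.
- Report adverse events and mortality descriptively, outside any adjustment.
- Report specific wound complications as risk differences with 95% confidence intervals, labelled descriptive.
- State that the multiplicity wording in the regression sentence applies to the risk-factor model, and name the method.

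The cost is wording only, with no new data, visits or patients. The sponsor gives up the right to call an isolated secondary p<0.05 significant and, if it takes the Holm route, accepts a stricter first threshold.
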